1.2 Secondary Objectives

Cohort A

- a. To estimate the 9 week response rate (RR) (unconfirmed complete and partial responses) among patients with measurable disease.
- b. To estimate the median overall survival (OS).
- c. To evaluate safety and tolerability of pembrolizumab (MK-3475) in the neoadjuvant setting.

Cohort B

- a. To estimate the median progression-free survival (PFS).
- b. To estimate the median overall survival (OS).
- c. To evaluate safety and tolerability of pembrolizumab (MK-3475) in this setting.
- 1.3 Other objectives (all patients)
 - a. To evaluate the hypothesis that higher mutational load in the patient derived baseline tumor biopsy samples is associated with higher pathologic complete response (pCR).
 - b. To evaluate T cell infiltration into the tumors and circulating tumor DNA profile from blood samples in DM patients and correlate with response to PD-1 blockade.
 - c. To evaluate the clonality of tumor infiltrating T cells in DM patients and correlate with response to PD-1 blockade.
 - d. To evaluate adaptive immune resistant mechanism in DM tumors.

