7.2 Treatment

a. Pretreatment Labs:

Blood samples collected for pretreatment laboratory tests may be collected and analyzed no more than 3 days prior to dosing at each cycle. Albumin, glucose, electrolytes (Na, K, HC03 or CO2), and thyroid function tests (T3, TSH and T4) are required to obtain baseline data for future toxicity assessments.

Cohort A: Pembrolizumab (MK-3475) for resectable disease

Agent	Dose	Route	Schedule
MK-3475 (pembrolizumab)	200 mg	IV over 30 minutes	Day 1, Q 3 weeks for 3 cycles *

¹ cycle = 21 days.

Pembrolizumab (MK-3475) treatment should be administered after all procedures and assessments have been completed. Pembrolizumab (MK-3475) treatment may be administered up to 3 days before or after the protocol-specified Q 3 weeks due to administrative reasons.

Pembrolizumab (MK-3475) treatment will be administered on an outpatient basis.

^{*} One additional cycle may be given for patients whose disease is unresectable after 3 cycles. See below.

Pembrolizumab (MK-3475) will be administered as a 30 minute IV infusion. Infusion timing should be as close to 30 minutes as possible; however, a window of -5 minutes and +10 minutes is permitted (*i.e.*, infusion time is 25-40 minutes).

- Disease assessment, using the same technique as baseline, will be performed every 9 weeks until discontinuation of protocol treatment.
 Patients with treatment delays may have additional disease assessments.
- After discontinuation of treatment, if the tumor is potentially resectable, the
 patients will proceed with surgical resection (see surgical guidelines below
 in Section 7.2). Pathology will be evaluated for evidence of pCR. If
 potentially resectable, surgery is required. This includes patients who have
 a complete response per RECIST 1.1 with no macroscopic evidence of
 disease.

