7.5 Criteria for Removal from Protocol Treatment – Cohort A

- a. Progression of disease (as defined in Section 10.0) that renders the patient unable to have disease resected.
- b. Patient chooses to proceed with surgical resection rather than continue on pembrolizumab.
- c. Unacceptable toxicity.
- d. The patient may withdraw from the study at any time for any reason.
- e. The investigator may discontinue treatment if they determine that the patient's continued treatment on the study is detrimental to their long-term health, or due to poor compliance with the study's required visits and treatments.
- Positive pregnancy test.
- g. Completion of protocol treatment (after resection).

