8.0 TOXICITIES TO BE MONITORED AND DOSE MODIFICATIONS

8.1 NCI Common Terminology Criteria for Adverse Events

This study will utilize the CTCAE (NCI Common Terminology Criteria for Adverse Events) Version 5.0 for toxicity and Serious Adverse Event reporting. A copy of the CTCAE Version 5.0 can be downloaded from the CTEP home page (http://ctep.cancer.gov). All appropriate treatment areas should have access to a copy of the CTCAE Version 5.0.

- 8.2 General Considerations
 - a. Missed doses of pembrolizumab should be made up.
 - b. Refer to Section 7.1 and 8.3a for supportive care information for pembrolizumab.
 - c. Dosing interruptions are permitted in the case of medical/surgical events or logistical reasons not related to study therapy (e.g., elective surgery, unrelated medical events, patient vacation, and/or holidays). Patients should be placed back on study therapy within 3 weeks of the scheduled interruption, unless otherwise discussed with the study chair. The reason for interruption should be documented in the patient's study record.
- 8.3 Pembrolizumab Dose Modification Guidelines for Drug-Related Adverse Events

Pembrolizumab must be withheld for drug-related toxicities and severe or life-threatening AEs as described below.

Adverse events (both nonserious and serious) associated with pembrolizumab exposure may represent an immunologic etiology. These immune-related AEs (irAEs) may occur shortly after the first dose or several months after the last dose of pembrolizumab treatment and may affect more than one body system simultaneously. Therefore, early recognition and initiation of treatment is critical to reduce complications. Based on existing clinical study data, most irAEs were reversible and could be managed with interruptions of pembrolizumab, administration of corticosteroids and/or other supportive care. For suspected irAEs, ensure adequate evaluation to confirm etiology or exclude other causes. Additional procedures or tests such as bronchoscopy, endoscopy, skin biopsy may be included as part of the evaluation. Based on the severity of irAEs, withhold or permanently discontinue pembrolizumab and administer corticosteroids. See Section 8.3a, Table 1, below.

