- b. Adverse Event Assessments on the study will continue for all patients until 30 days after the last study drug administration. However, patients with ongoing toxicities should be seen more often as clinically indicated.
- c. Post-treatment (after receiving the final dose of pembrolizumab on study) follow-up (prior to progression/relapse): Patients should be seen at 6 weeks (-/+ 1 week) after the last dose, then every 12 weeks (+/- 2 weeks) to the end of the first year after registration, then every 6 months (+/- 4 weeks) to the end of the fifth year after registration.
- d. After progression patients should be followed every 6 months for up to 2 years from the date of treatment registration, then annually thereafter until 5 years from treatment registration.
- e. While on study, blood samples collected for pretreatment laboratory tests may be collected and analyzed no more than 3 days prior to dosing. NOTE: if MK-3475 was delayed per the dose delay/scheduling criteria or if a visit had to be delayed due to major circumstances (such as a health emergency, family/personal emergency, transportation difficulties, scheduling difficulties, a visit date falls on a holiday), the study assessments scheduled for these dates will be delayed.
- f. LDH to be done at screening and at progression/relapse. If patient has a subsequent scan 4 weeks later that does not document progression, following an initial progression while on protocol therapy do not need to have LDH done at this time.
- h. ECG to be performed at baseline, then as clinically indicated.
- i. Women of childbearing potential must have a negative serum or urine pregnancy test within 28 days prior to registration. Following randomization, serum or urine pregnancy tests are required within 72 hours prior to the first dose of study treatment, then according to institutional practice during therapy, tests should coincide with clinic visits for blood work and ending with the discontinuation of study treatment. At discontinuation, a negative pregnancy test within the preceding 6 weeks is sufficient. A pregnancy test should be done at any time there are clinical concerns for possible pregnancy.
- j. Patients with primary melanoma of the head and neck will also require a neck CT.

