- k. For patients who have not progressed/relapsed, disease assessments by CT (or MRI if CT cannot be done) chest/abdomen/pelvis or whole body PET-CT will be performed at Week 9 (at end of neoadjuvant therapy) and then imaging studies may be done as clinically indicated at the discretion of the treating investigator.
- o. Thyroid function tests to include TSH, Free T3, and Free T4 must be performed prior to initiating treatment (within 3 days prior to initial dose on Cycle 1) as a reference, should hypothyroidism symptoms arise during treatment. TSH is to be performed prior to dose at week 7, and at initial post treatment follow-up. Additional testing of Free T3 and Free T4 should be performed as clinically indicated if TSH is abnormal or if symptoms are suggestive of thyroid dysfunction.
- p. If a skin lesion is a site of disease, photographs (with a ruler in the photo if the lesion is measurable per RECIST 1.1) must be taken as documentation. Physician's report and photograph must be stored in the patient's chart as source documentation. In addition, the physician's report must be uploaded into Medidata Rave (see Section 14.0). In addition, abnormal lesions concerning for basal cell or squamous cell should be documented in the physician's report and, if biopsy obtained, the pathology report should be included in the patient's chart as source documentation.
- q. See the third bullet under Section 7.1b If after the first disease assessment, the tumor is unresectable, treatment will continue for 1 more cycle and a repeat disease assessment using the same technique as baseline will be obtained 4 weeks later. If at this time the patient's disease is deemed resectable, the patient must continue with resection as previously planned.
- r. History prior to each treatment initiation to include a menstrual, sexual and contraceptive use history, including date of last menstrual period (for women of childbearing potential) which will help determine the need for pregnancy testing. Similar questions regarding contraceptive use should be asked of men who are sexually active with women of childbearing potential. Height is only required at baseline.

Footnotes for Study Calendar 9.1 (contd.): Pembrolizumab (MK-3475)

- s. As the primary endpoint of the study is pCR and the goal of the surgery is to remove visible and microscopic disease, surgery is required for all potentially resectable tumors. If the tumor is deemed unresectable at 9 weeks, a biopsy should be obtained.

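### Routine adverse event assessment closes 30 days after the last dose, before the first follow-up visit at which it is marked and possibly before resection in Cohort A, so late and perioperative toxicity may be under-recorded

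*Combined protocol and SAP*

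**What the plan says.** - **AE window.** Calendar footnote b, in both cohorts: "Adverse Event Assessments on the study will continue for all patients until 30 days after the last study drug administration". It adds that "patients with ongoing toxicities should be seen more often as clinically indicated", but sets no visit for them and no longer window for new events.
- **First follow-up visit.** Footnote c: "Patients should be seen at 6 weeks (-/+ 1 week) after the last dose". Both calendars mark AE notation in the follow-up columns. The column for follow-up before progression also carries blood counts, bilirubin, liver enzymes and creatinine, and footnote o adds TSH at the first such visit.
- **Patients who stop for toxicity.** In Cohort A, footnote u sends them to the follow-up column instead of the end-of-treatment assessment.
- **Surgery in Cohort A.** Dosing is "Day 1, Q 3 weeks for 3 cycles", with a possible fourth. Surgery follows the disease assessment if the tumor is potentially resectable. The Surgical Resection column shows no AE mark, and no interval from last dose to surgery is given. Section 7.5g places completion of protocol treatment after resection, and Section 14.4f asks for an AE Form within 7 days of ending protocol treatment.
- **Why it matters to the plan.** Section 1.2 has the Cohort A objective "To evaluate safety and tolerability of pembrolizumab (MK-3475) in the neoadjuvant setting". Section 11.1b makes the recommendation for further study conditional on acceptable toxicity. Section 8.3 says immune-related events can arise "several months after the last dose of pembrolizumab treatment".

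**The concern.** Two instructions in the same calendar do not fit together. AE notation is marked at a visit that, on schedule, always falls after assessment has closed. Tests that could reveal thyroid, liver, renal or hematologic toxicity are done at that visit, yet a newly arising, non-serious Grade 1 or 2 abnormality found there has no clear route into the AE data.

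In Cohort A the same cut-off can fall around or before resection. Footnote b then closes assessment while the patient is still on protocol treatment under Section 7.5g, whereas Section 14.4f implies an AE Form after resection. Sites could resolve this differently, and recording would then vary by site. At stake are how complete the toxicity summary is for a secondary objective, and the informal toxicity condition on the Section 11.1b recommendation. The primary endpoint is not affected.

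**Working it through.** **1. The plan's own toxicity figures.** Section 11.1d gives a 72.3% chance of seeing at least once, in 25 patients, a toxicity with 5% incidence: 1 − 0.95^25 = 0.7226. It gives precision of 19.6%: 1.96 × √(0.25/25) = 0.196. Both reproduce. Read as statements about all pembrolizumab toxicity, they presume that every event is recorded. The issue is recording, not calculation.

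**2. Window against first follow-up visit (footnotes b and c, both cohorts).** 6 weeks ± 1 week = 42 ± 7 = 35 to 49 days after the last dose. The window closes at day 30. Gap: 35 − 30 = 5 days at the earliest, 42 − 30 = 12 nominally, 49 − 30 = 19 at the latest.

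**3. Three cycles in Cohort A (no delays, first dose on Day 1).**
- Doses on Days 1, 22 and 43, so the window closes on Day 43 + 30 = 73.
- Read as nine completed weeks (footnote a ties the scan to the end of three cycles), the assessment is on Day 1 + 63 = 64, leaving 73 − 64 = 9 days.
- On the calendar's own numbering, where Week 7 is Day 43, Week 9 begins on Day 57, leaving 73 − 57 = 16 days.
- First follow-up visit: Day 43 + 35 to 43 + 49 = Days 78 to 92.

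Surgery and any recorded recovery must therefore fit into about 9 to 16 days after the assessment to be inside the window.

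**4. Four cycles in Cohort A.** The fourth dose is on Day 64 and the window closes on Day 64 + 30 = 94. Section 7.2 sets the repeat assessment at 28 ± 7 days. Assuming this is counted from the fourth dose, it falls on Days 85 to 99. Time left at that assessment: 94 − 85 = 9 days, 94 − 92 = 2 days nominally, 94 − 99 = −5 days. Surgery comes later still.

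**5. What is still collected after day 30.**
- Table 16.1, footnote 1: serious events with possible, probable or definite attribution, if Grade 3 to 5, or Grade 2 with hospitalization.
- Section 14.4i: Late Effects Form for Grade 3 or higher long-term toxicity not already reported, to 5 years, before non-protocol treatment or treatment for progression, relapse or a second primary.
- Section 14.4f with 7.5g: an AE Form, which in resected Cohort A patients falls after resection.
- Section 14.4h: operative and pathology reports within 14 days of surgery.

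What routine collection leaves out is new Grade 1-2 immune-related events (apart from the attributed Grade 2 serious events above) and perioperative events that are non-serious or not attributed to the drug. Section 11 does not say whether Late Effects or post-day-30 expedited reports enter the toxicity summary.

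**6. Illustration only.** The documents give no distribution of onset times. Assume a toxicity with 5% total incidence, of which a share f starts inside the window. The chance that routine assessment sees it at least once in 25 patients is 1 − (1 − 0.05f)^25:
- f = 1: 72.3%
- f = 0.9: 68.4%
- f = 0.75: 61.5%
- f = 0.5: 46.9%
- f = 0.25: 27.0%

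These values show sensitivity to f. They do not estimate the loss in this trial.

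**The case against.** A reader might infer that surgical complications and late immune events go unrecorded, and that toxicity rates are therefore biased low. The documents do not support this. Severe and attributed serious events remain reportable after day 30, an AE Form is due after resection, and operative reports are submitted. The direction of risk is toward under-recording, but without onset data no bias can be claimed as established or sized. A rate through 30 days after the last dose is also a defined quantity, it matches the main expedited-reporting window in Table 16.1, and the protocol states no surgical-complication endpoint.

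Two further points are fair. A visit at days 35 to 49 could sensibly record events that began by day 30, so the AE mark need not be a strict contradiction. And the superscripts on the marks in calendar 9.1 are hard to read, although the Cohort B row label carries b legibly. On either reading, however, an event that starts after day 30 and is found at that visit has no clear routine place. The conflict between footnote b and the post-resection AE Form also remains, because Section 14.4f does not say which period that form covers.

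Finally, Cohort A patients who stop in preparation for surgery do have an end-of-treatment assessment with AE notation. Those who stop for toxicity do not, because footnote u sends them to the later column. Calendar 9.2 has no such assessment at all.

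**Conclusion.** The concern holds as a gap in routine collection and a need to reconcile the text. On schedule, the first follow-up visit falls 5 to 19 days after AE assessment closes, in both cohorts. In Cohort A the window leaves about 9 days after a Day 64 assessment (16 if Week 9 means Day 57), and from 9 days to none after the repeat assessment that follows a fourth cycle. These figures assume no dose delays and, for the fourth cycle, that the interval is counted from that dose. Whether resection falls inside the window cannot be determined, because no interval to surgery is stated.

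Late Grade 1-2 immune-related events, and non-serious or unattributed perioperative events, may be under-ascertained by an amount the documents do not allow to be estimated. The change is worth making for objective 1.2c and the toxicity condition in Section 11.1b. It does not touch the design or the pathologic complete response analysis.

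**What to change.** - Change footnote b in calendars 9.1 and 9.2 so that AE notation runs through the first scheduled post-treatment follow-up visit (6 weeks ± 1 week after the last dose).
- For resected Cohort A patients, continue it through the first already scheduled follow-up visit after resection.
- Reconcile footnote b with Section 14.4f, stating the period that the AE Form after resection covers.
- In the Section 11.1 toxicity summary, report events before and after surgery separately, and include Late Effects and post-day-30 expedited reports.

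A fixed 30-day window after resection is tempting but matches no scheduled visit, because follow-up is counted from the last dose. For example, surgery on Day 75 would put that point on Day 105, whereas visits fall on Days 78 to 92 and then about 12 weeks later. Anchoring to existing visits avoids a new contact.

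**Cost.** A few more AE form entries, and no new visits or tests. Events between visits would rest partly on recall: if surgery follows the first visit, the next is about 12 weeks after that visit. If surgery comes shortly before a visit, the added postoperative coverage is short (75 to 78 is 3 days in the example). Rates would be less directly comparable with those from a 30-day window, so events within 30 days of the last dose should remain identifiable.

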9.2 Pembrolizumab (MK-3475)-Cohort B

REQUIRED STUDIES	Pre-study (screening ^{s)}	Each cycle o	ON TREA consists of 1 ir given q 3 w	Post treatment F/U prior to progression °	Post treatment F/U post progression ^d		
		Cycle 1 Week 1 *	Cycle 2 W4 *	Cycle 3 W7*	Cycle 4+		
PHYSICAL							
History & Physical, PS (w/BP, Weight) ^r	Х	Х	Х	00,	х	х	Х
Adverse Event Notation ^b		Х	Х	Х	Х	Х	X
Skin exam ^p	Х	Х	Х	X	Χq	Χq	
Baseline Abnormalities	Х	X	1/1				
LABORATORY ^e		ć					
ANC, platelets, Hgb	X	X.	X	Х	Х	X	
Total bilirubin	X	X	Х	X	Χ	X	
LDH ^f	X						X
AST, ALT, and Alkaline Phosphatase	Х	Х	×	X	Х	X	
Serum Creatinine or CrCl	X	Х	X	X	X	X	
Albumin, Glucose, Na, K, HCO3/CO ₂		X	×	X	Х	X	
Thyroid function tests °		X		X	Χ°	Χ°	X
Pregnancy Test ⁱ	×	X	X	X	X		X

Click here for footnotes.

Study Calendar 9.2 continued on next page.

REQUIRED STUDIES	Pre-study ^s	Each cyc	cle consists o	EATMENT f 1 infusion. Infu j 3 weeks. ^{a q}	Post treatment F/U prior to progression ^c	Post treatment F/U post progression ^d	
	(Screening)	Cycle 1 W 1 *	Cycle 2 W 4 *	Cycle 3 W 7 *	Cycle 4+ a	2	
PHYSICAL						70	
X-RAYS AND SCANS					. \\)	
CT ^j , chest, abdomen & pelvis or whole body PET/CT ^k	Х			0	XV	X k	X ^t
Brain MRI or CT with contrast kh	Х			- 11			
EKG ^h	Х						
SPECIMEN SUBMISSION				U O.			
Tissue w	X		X				X (optional)
Whole Blood ^u	Х		.<	/ .			
TREATMENT			- 1				
Pembrolizumab (MK-3475)		Х	X	X	Х	_	

Click here for footnotes.

NOTE: Forms are found on the protocol abstract page of the SWOG website (www.swog.org). Form submission guidelines are found in Section 14.0.

NOTE: Unless indicated otherwise in the protocol, scheduled procedures and assessments (treatment administration, toxicity assessment for continuous treatment, disease assessment, specimen collection and follow-up activities) must follow the established SWOG guidelines as outlined in

https://swog.org/Visitors/Download/QA/Best%20Practices%20upddate.pdf.

Footnotes for Study Calendar 9.2: Pembrolizumab (MK-3475)

- a. Treatment will continue every 3 weeks, with scans after each 3 cycles (9 weeks). Protocol treatment and parameters will continue on the same schedule until patient has met any of the criteria in Section 7.5. If disease becomes resectable, see surgical guidelines under Section 7.2 and also 14.4h.
- b. Adverse Event Assessments on the study will continue for all patients until 30 days after the last study drug administration. However, patients with ongoing toxicities should be seen more often as clinically indicated.
- c. Post-treatment follow-up (prior to progression/relapse): Patients should be seen at 6 weeks (-/+ 1 week) after the last dose, then every 12 weeks (+/- 2 weeks) to the end of the year after registration, then every 6 months (+/- 4 weeks) to the end of the fifth year after registration.
- d. After progression patients should be followed every 6 months for up to 2 years from the date of treatment registration, then annually thereafter until 5 years from treatment registration.
- e. While on study, blood samples collected for pretreatment laboratory tests may be collected and analyzed no more than 3 days prior to dosing. NOTE: if MK-3475 was delayed per the dose delay/scheduling criteria or if a visit had to be delayed due to major circumstances (such as a health emergency, family/personal emergency, transportation difficulties, scheduling difficulties; a visit date falls on a holiday), the study assessments scheduled for these dates will be delayed.
- f. LDH to be done at screening and at progression/relapse. If patient has a subsequent scan 4 weeks later that does not document progression, following an initial progression while on protocol therapy, they do not need to have LDH done at this time.
- h. To be performed at baseline, then as clinically indicated throughout treatment.
- i. Women of child bearing potential must have a negative serum or urine pregnancy test within 28 days prior to registration. Following randomization, serum or urine pregnancy tests are required within 72 hours prior to the first dose of study treatment, then according to institutional practice during therapy, tests should coincide with clinic visits for blood work and ending with the discontinuation of study treatment. At discontinuation, a negative pregnancy test within the preceding 6 weeks is sufficient. A pregnancy test should be done at any time there are clinical concerns for possible pregnancy.
- j. Patients with primary melanoma of the head and neck will also require a neck CT
- k. Disease assessments by CT (or MRI if CT cannot be done) chest/abdomen/pelvis or whole body PET/CT will be performed every 9 weeks until disease progression. During treatment and follow-up, brain MRI/CT or other imaging studies may be done as clinically indicated but are not required in the absence of clinical indications.
- o. Thyroid function tests to include TSH, Free T3, and Free T4 must be performed prior to initiating treatment (within 3 days prior to initial dose on Cycle 1) as a reference, should hypothyroidism symptoms arise during treatment. TSH is to be performed prior to dose at week 7, and at initial post treatment follow-up. Additional testing of Free T3 and Free T4 should be performed as clinically indicated if TSH is abnormal or if symptoms are suggestive of thyroid dysfunction.
- p. If a skin lesion is a site of measurable disease, photographs (with a ruler in the photo if the lesion is measurable per RECIST 1.1) must be taken as documentation. Physician's report and photograph must be stored in the patient's chart as source documentation. In addition, the physician's report must be uploaded into Medidata Rave (see Section 14.0). In addition, abnormal lesions concerning for basal cell or squamous cell should be documented in the physician's report and, if biopsy obtained, the pathology report should be included in the patient's chart as source documentation. If the skin lesion is the site of measurable disease, measurements should be taken after 3 cycles (9 week intervals).
- q Patients may continue protocol treatment following progression if they are still deriving clinical benefit in the opinion of the treating investigator.
- r. History prior to each treatment initiation to include a menstrual, sexual and contraceptive use history, including date of last menstrual period (for women of childbearing potential) which will help determine the need for pregnancy testing. Similar questions regarding contraceptive use should be asked of men who are sexually active with women of childbearing potential. Height is only required at baseline.
- s. Pre-study labs, MRI brain, and ECG should be obtained within 28 days prior to registration.
- t. Survival data are to be collected. Scans obtained in post-treatment F/U post progression, are at the clinical discretion of the treating physician and do not need to be submitted into the EDC system.
- u. Whole blood must be collected prior to protocol treatment (mandatory).
- w. Please see Section 15.1 for FEPE submission for translational medicine and Section 15.2 for additional submission of slides for pathology review.
- y. Scans will be obtained every 9 weeks for the first 6 months, then every 4 months.
- * These are the corresponding weeks if there are no dose delays.

